## ***Measures***

### ***Questionnaires***

The following PE teachers' variables will be measured using Google Forms before the training program (T1), as well as during (T2) and at the end of the implementation of the intervention with their students (T3) (see Figure 1):

**Socio-demographic variables.** Age, gender, teaching experience, type of school (public or private), and school location (rural or urban) will be self-reported by teachers.

**(De)motivating teaching styles and approaches towards students.** To assess self-reported (de)motivating teaching styles toward students, the Spanish version of the SIS in Physical Education (SIS-PE; (Burgueño, Abós, et al., 2024) will be used. The SIS-PE comprises 12 typical teaching situations consisting of four items each (i.e., 48 items). Autonomy-supportive items are categorised into participative (four items) and attuning (eight

items) approaches. Structure items are operationalised into guiding (seven items) and clarifying (five items) approaches. Control items are divided into demanding (seven items) and domineering (five items) approaches. Chaos items are operationalised into abandoning (eight items) and awaiting (four items) approaches. For instance, this situation “At the start of class...” is followed by four items: you can explore students’ prior knowledge of the topic (attuning), set up a class clearly and straightforwardly (clarifying), demand application of what’s taught (demanding), or just begin and let the class evolve (awaiting)”. It should be noted that, since teachers’ perceptions of their (de)motivating teaching styles could be different according to the classroom group, teachers will have to answer the questionnaire taking into account the groups of students selected for the study. Teachers’ responses will be assessed using a 7-point Likert scale ranging from 1 (“Does not describe me at all”) to 7 (“Describes me perfectly”).

**Autonomy and competence satisfaction and frustration at work.** To assess PE teachers’ perceptions of autonomy and competence satisfaction and frustration at work, the Spanish version of the Basic Psychological Needs at Work Scale for in-service teachers (Abós Catalán et al., 2018) and the Basic Psychological Need Satisfaction and Frustration Scale (Chen et al., 2015), will be used, respectively. Four of the six factors of these scales will be assessed, except relatedness satisfaction and frustration. Both scales are preceded by the stem “In my job as a PE teacher...” assessing autonomy satisfaction (Four items; e.g., “My job allows me to make decisions”), autonomy frustration (Four items; e.g., “I feel that most of the things I do in my job, I do them because I have to do them”), competence satisfaction (Four items; e.g., “I have the ability to do my job well”), and competence frustration (Four items; e.g., “I have serious doubts that I can do well in my job”). Teachers’ responses will be assessed using a 5-point Likert scale ranging from 1 (“strongly disagree”) to 5 (“strongly agree”).

**Job satisfaction at work.** Teachers' perceptions of job satisfaction at work will be assessed using a Spanish translation (Abós et al., 2019) of the Teacher Job Satisfaction Scale (TJSS; Skaalvik & Skaalvik, 2011). This four-item scale includes one single factor (e.g. "I enjoy working as a teacher"). Teachers' responses will be registered on a 6-point Likert scale from 1 ("strongly disagree") to 6 ("strongly agree").

**Emotional exhaustion at work.** Teachers' emotional exhaustion will be assessed using the Spanish version of the Maslach Burnout Inventory-General Survey (Gil-Monte, 2002). In line with other studies on PE teachers (Richards et al., 2019), only the five items assessing the exhaustion factor will be used in the present study (e.g., "I feel burned out from my work"). Teachers' responses will be reported on a 7-point Likert scale from 0 ("never") to 6 ("every day").

**Job performance.** Teachers' perceptions of their professional performance will be assessed using the following sentence: "Rate your satisfaction with your professional performance this academic year", which has been previously used in other studies (Barrick et al., 2002). Teachers' responses will be provided on a 9-point Likert scale, ranging from 1 ("non-existent") to 9 ("excellent").

**Quality of the training program.** Consistent with previous studies (Aelterman et al., 2013; Cheon & Reeve, 2015; Slingerland et al., 2017), a short paper-and-pencil questionnaire will also be measured immediately after each session of the training program carried out to gain insight into their content. Questions will be related to: (1) Interaction, (2) innovation, (3) interest, (4) intelligibility, (5) essentiality, (6) practical usefulness, (7) feasibility of the motivating strategies, (8) intention to implement the motivating strategies, (9) the extent to which one would recommend the training to others, (10) perceived changes in their (de)motivating styles, and (11) overall satisfaction. This questionnaire will be rated on a 5-point Likert scale from 1 (totally disagree) to 5 (totally agree), except for the last question, in

which teachers will rate the overall satisfaction on a scale from 1 to 10. Lastly, in an open-ended question, teachers will be able to detail the strengths and areas for improvement in each of the sessions to make slight adjustments to the training program in their future implementation.

Like their teachers, students will fill out the following questionnaires before the training program (T1), as well as during (T2) and at the end of the implementation of the intervention by the PE teachers (T3) (See Figure 1). Depending on the protocol of each school, these questionnaires will be completed in paper-and-pencil format or using Google Forms in a quiet classroom environment. The PE teacher will not be present when their students complete the questionnaires to avoid bias in the responses. In this sense, a member of the research will help the students with any doubts that may exist.

**Socio-demographic variables.** Age, gender, and school grade level will be self-reported by students.

**(De)motivating teaching styles and approaches.** To assess students' perceptions of (de)motivating teaching approaches of their PE teachers, the Spanish version of students of the Situations-in-School Questionnaire in Physical Education (SIS-PE; (Burgueño, Abós, et al., 2024) will be used. The only change in the instrument compared to the teachers' instrument is the structure of the sentences, as they are written from the students' perspective (e.g., "Your teacher invites you to suggest a set of norms or rules").

**Autonomy and competence satisfaction and frustration in PE.** To assess students' perceptions of autonomy and competence satisfaction in PE, the Spanish version (Zamarripa et al., 2020) of the Basic Psychological Need Satisfaction and Frustration Scale (Chen et al., 2015) will be used. Four of the six factors of these scales will be assessed, except relatedness satisfaction and frustration in PE. Preceded by the stem "In mi PE lessons...", the 16 items (four items per factor) assessing autonomy satisfaction (e.g., "I feel I have been doing what

interests me”), autonomy frustration (e.g., “I feel pressured to do too many tasks”), competence satisfaction (e.g., “I feel I can complete difficult tasks”), and competence frustration (e.g., “I feel like a failure because of the mistakes I make”). Items will be assessed using a 5-point Likert scale ranging from 1 (strongly disagree) to 5 (strongly agree).

**PE experiences.** In line with previous research (Diloy-Peña et al., 2024), students’ perceived experiences in PE classes will be assessed using the question: “What are your experiences in PE lessons like?” The response possibilities were: (1) “very bad”, (2) “bad”, (3) “neutral”, (4) “good”, and (5) “very good”.

**Perceived learning in PE.** In line with previous research (Diloy-Peña et al., 2024), students’ perceptions of learning in PE will be assessed using the question: “How much do you learn in PE?” The response possibilities will be on a scale from 1 (“nothing”) to 5 (“a lot”).

**Intention to be physically active.** Students’ perceptions of intention to participate in PA will be assessed using three items (e.g. “I intend to do active sports and/or physical activities during my leisure time in the next 5 weeks...”) of the Spanish version of the Theory of Planned Behaviour Questionnaire (Tirado-González et al., 2012). This is a 5-point Likert scale from 1 (“strongly agree”) to 7 (“strongly disagree”).

### ***Observation***

**Observed (de)motivating teaching styles and approaches.** Before the study, two raters with expertise in PE teaching instruction and the circumplex model will be trained in how to code (de)motivating teaching styles and approaches during PE using a Spanish translation of the SIS-PE-Coder, a new observation instrument that showed good reliability and internal validity (Van Doren et al., 2023). Following Van Doren et al. (2023) procedure, two randomly selected five-minute videos will be coded, trying to represent the beginning, middle or end of the lesson during six meetings. Before the final meeting, each expert

independently will code an entire lesson. Interobserver reliability was determined through Cohen's Kappa, using the following formula: agreements / (agreements + disagreements) × 100.

Consistent with the teachers' version of the SIS-PE, the SIS-PE-Coder consists of 41 items of which four items represent the participative approach, five items the attuning approach, six items the guiding approach, five items the clarifying approach, five items the demanding approach, seven items the domineering approach, five items the abandoning approach, and five items the awaiting approach. The coder will be prompted to assess each teaching behaviour from students' perspective, as specified by the statement: "If you were a student in this PE class, you would believe that the PE teacher...". Each item will be coded on a 7-point Likert scale, ranging from 0 (does not display this behaviour) to 6 (perfectly displays this behaviour). Two classes per experimental group teacher will be recorded by these two raters at two different moments of the implementation phase (before the second and third quantitative measures; See Figure 1). Items will be coded at 5-minute intervals (Aelterman et al., 2013). For every lesson, interval scores will be added together to create a sum score for each teaching behaviour throughout the entire duration of the lesson. This sum will be divided by the number of coded 5-minute intervals. Subsequently, scores for (de)motivating teaching styles, as well as the eight approaches, will be generated by averaging the scores of the individual items corresponding to each of the four styles and eight teaching approaches. The aim of the recordings will be not only to assess the fidelity of the intervention but also to provide opportunities for teachers to self-assessment, as well as co-assessment by a member of the study.

For the observational analysis recordings, various professional video cameras will be used, as well as microphones connected to both the camera and the PE teacher who will be

conducting the lessons. For digitizing the video from the start to the end of the PE class, the iMovie (IOS) program will be used.

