## **Materials and methods**

### ***Context, design, and randomization***

[figure not shown]
This study will be carried out in a northeast region of Spain [details masked for review process]. PE is mandatory for every secondary school student in Spain. Each student receives two 50-minute coeducational PE lessons per week. Spanish Secondary PE teachers are expected to teach between 18 and 21 hours per week. Typically, the annual teaching plan of PE teachers includes approximately six to eight distinct teaching units per year. These units encompass various content types such as individual, cooperative, and interactive sports and games, as well as body expression, health-related fitness, and outdoor activities, all of which are outlined in the PE curriculum. The academic year lasts from September to June, divided into three terms, each separated by a holiday period (i.e., Christmas and Easter).

A randomized controlled trial design with a mixed-method approach will be carried out. PE teachers agreeing to participate in the trial will be randomly assigned to either the experimental or the control group. Randomization will be conducted using the digital tool available at <https://echaloasuerte.com/>. To prevent contamination of the experimental condition, schools will only participate in one group (i.e., experimental or control). Subsequently, at least two groups of students from each PE teacher will be randomly selected.

This study will comprise two phases: 1) a teacher-training phase and 2) an implementation phase with students. It should be noted that the training program will continue with some individual and group sessions during the implementation phase. Since teachers' and students' perceptions of (de)motivating teaching styles and approaches and other study variables require several months for greater accuracy in their perceptions, the

training program will not start until the second term of the academic year (for more details see Figure 1).

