This study will provide a unique contribution to knowledge in ten key areas: (1) it will be the first motivational training program based on the recent circumplex model, due to the recent and innovative nature of this approach, and the eight teaching approaches proposed by the circumplex model will be assessed using real-life educational situations thought the SIS-PE instrument; (2) the quality of each face-to-face training session and follow-up sessions of the training program will be examined through short questionnaires at the end of each class, as well as a focus group with the entire PE teachers; (3) the effects of the intervention on a wide range of study variables will be evaluated using a mixed-method approach (i.e., questionnaires and focus groups) in both teachers and students; (4) the effects of the intervention on boys and girls students and male and female teachers will be examined; (5) not only a post-test, but also an intermediate measure will be used to examine how the study variables vary throughout the program; (6) the training program will not only take place before the implementation of the intervention, but also during the intervention; (7) the training program will include two individual and group follow-up sessions in which constructive feedback will be provided, as well as an individualized report; (8) promising strategies that have been shown to be effective in previous SDT-training programs (e.g., congruent style, brief theoretical part, real videos of PE teachers, microteaching, co-creation of teaching strategies, etc.) will be used; (9) the assessment of intervention fidelity through a new validated observational instrument in line with the circumplex model (i.e., SIS-PE-Coder) will be used; (10) MBCTs provided by Ahmadi et al. (2023) will be used in the development of the intervention implementation to find out to which behaviour change techniques are attributed to the intervention effects.

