be considered. Secondly, observation will be used twice to ensure intervention fidelity and provide constructive feedback to teachers during the intervention but will not be used as a complementary measure of students' and teachers' perception of (de)motivating teaching styles in the three measures of the study due to lack of human resources. Thirdly, teachers' perceptions of their beliefs regarding (de)motivating teaching styles will not be assessed by means of questionnaires due to their length, as well as the absence of validated instruments of control and chaos styles. Additionally, relatedness satisfaction and frustration at work will not be assessed because the training program will not target teachers within the same school. Additionally, teachers' perceptions of depersonalization and reduced personal accomplishment (i.e., burnout factors) will not be assessed using questionnaires due to their length. However, all these variables will be assessed through the focus groups to obtain more information on the effects of the training program and the subsequent intervention carried out. Finally, students' perceptions of relatedness satisfaction and frustration in PE will not be assessed employing questionnaires due to their length and because the teacher training program was based on the circumplex model, which does not address the need for relatedness. As a final limitation, it is very likely that a post-intervention follow-up measure cannot be carried out the following academic year because in Spain it is very common for teachers to change schools every year. Therefore, it will only be possible to assess students' perception of the study variables if the teacher is the same. Similarly, the perception of (de)motivating teaching style might change with different classroom groups.

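### The formula printed for Cohen's kappa is percent agreement, so coder reliability computed as written would carry the wrong name

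*Protocol*

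**What the plan says.** The Observation subsection describes how two raters are trained on the SIS-PE-Coder before the study. Near the end of that training each rater "independently will code an entire lesson". The protocol then states: "Interobserver reliability was determined through Cohen's Kappa", and the same sentence supplies the definition: "Kappa, using the following formula: agreements / (agreements + disagreements) × 100".

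On the data to be compared, it says "Each item will be coded on a 7-point Likert scale, ranging from 0 (does not display this behaviour) to 6 (perfectly displays this behaviour", and "Items will be coded at 5-minute intervals". It does not say whether two codes agree only when identical or also when close. It gives no weights, no acceptance threshold and no other formula for kappa.

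On the use of the instrument, the Discussion lists among the study's contributions "the assessment of intervention fidelity through a new validated observational instrument in line with the circumplex model", and the Limitations state that "observation will be used twice to ensure intervention fidelity".

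**The concern.** The sentence names one statistic and defines another. Cohen's kappa removes the agreement expected by chance from the raters' category frequencies. The printed expression only counts matches and rescales them to 0–100.

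The difference matters most when one code dominates, because chance agreement then rises. That could happen here: code 0 means the behaviour is not displayed, and many behaviours may be absent from a given five-minute interval. Two raters could then match often without distinguishing the behaviours that do occur.

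What is at stake is the credibility of the fidelity evidence. The reliability figure is the protocol's own evidence that these two coders apply the instrument consistently, and a reader who sees kappa will take it as chance-corrected.

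**Working it through.** The protocol states no reliability value, so there is no figure to reproduce. The check compares the two definitions and then illustrates the gap.

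**Definitions.** Let Po be the observed proportion of agreement and Pe the proportion expected by chance (the sum over codes of the product of the two raters' shares).

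- Printed formula: 100 × A/(A + D) = 100 × Po.
- Unweighted kappa: (Po − Pe)/(1 − Pe).
- Difference on the 0–1 scale: Po − kappa = Pe(1 − Po)/(1 − Pe). This is positive whenever agreement is imperfect and Pe > 0.

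**Inputs from the protocol.** Two raters, and seven ordered codes, 0 to 6.

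**Assumptions, not from the protocol.** Both raters have the same share of zeros, p0, and the other six codes share the remainder equally. Then Pe = p0² + 6 × ((1 − p0)/6)². For p0 = 0.70, Pe = 0.49 + 6 × 0.05² = 0.505.

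| Share of zeros | Pe | Printed figure if agreement is by chance only (kappa = 0) | Kappa at Po = 0.80 | Gap |
|---|---|---|---|---|
| 1/7 (even use) | 0.143 | 14.3 | (0.80 − 0.143)/0.857 = 0.77 | 0.03 |
| 0.70 | 0.505 | 50.5 | (0.80 − 0.505)/0.495 = 0.60 | 0.20 |
| 0.80 | 0.647 | 64.7 | (0.80 − 0.647)/0.353 = 0.43 | 0.37 |

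The zeros alone force agreement of at least max(0, 2p0 − 1) = 0, 0.40 and 0.60 in the three rows, so 80% agreement is not a boundary case in any of them.

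**If codes within one point count as agreement.** Chance agreement becomes 0.388, 0.600 and 0.711. A printed 80 then corresponds to chance-corrected values of (0.80 − 0.388)/0.612 = 0.67, (0.80 − 0.600)/0.400 = 0.50 and (0.80 − 0.711)/0.289 = 0.31. The same printed number thus has a different meaning under each reading of agreement.

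**Weighted kappa.** With equal marginals, quadratic-weighted kappa = 1 − (1 − Po) × d/(2 × variance), where d is the mean squared distance among disagreements. For p0 = 0.70 the mean code is 0.05 × 21 = 1.05, the mean square is 0.05 × 91 = 4.55, the variance is 4.55 − 1.05² = 3.4475, and twice that is 6.895. At Po = 0.80:

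- all disagreements one point apart (d = 1): 1 − 0.2/6.895 = 0.97
- two points apart (d = 4): 1 − 0.8/6.895 = 0.88
- three points apart (d = 9): 1 − 1.8/6.895 = 0.74

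The statement that the printed figure overstates kappa therefore applies to the unweighted coefficient only.

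**Paired codes available.** Context, design, and randomization states: "Each student receives two 50-minute coeducational PE lessons per week". A 50-minute lesson has 50/5 = 10 intervals, and 10 × 41 items = 410 codes per rater. The eight item counts listed by approach add to 4 + 5 + 6 + 5 + 5 + 7 + 5 + 5 = 42, not 41, which would give 420. Either count assumes that the whole lesson is coded and that both raters code the same lesson, as an interobserver figure requires.

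**The case against.** The strongest reply is that little depends on this figure. The hypotheses rest on teacher and student perceptions. The quantitative analysis plan does not analyse the observational scores, only experimental-group teachers are recorded, and the Limitations exclude observation as a complementary measure at the three time points. That stands, and it limits the consequence to reliability and fidelity reporting.

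Second, the reliability sentence sits in the account of rater training, and the protocol does not say that the coefficient is computed on the trial recordings. This also stands: the figure describes the coders, and bears on fidelity through them.

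Third, kappa may be computed in software, with only the formula misprinted, and a value such as 80 would visibly not be a kappa. Both are possible. The criticism is of the calculation as written; even if it is only a misprint, someone replicating the study could not tell which statistic to compute.

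Fourth, the category shares are assumed, and a weighted kappa can exceed the percent agreement. Both are correct, so the defect is a wrong label, not a demonstrated inflation of reliability.

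Finally, the definition of an agreement and the choice of weights are details that could sit in a coding manual or a statistical analysis plan. They are secondary here. The mismatch between the name and the formula does not depend on them.

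**Conclusion.** The point holds. The protocol names Cohen's kappa and defines percent agreement in the same sentence, and nothing elsewhere overrides it. Followed as written, the rule yields a statistic that is not the one named.

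The size of the discrepancy cannot be determined from the protocol. At 80% exact agreement, the gap from unweighted kappa would be 0.03, 0.20 or 0.37 under the three assumed code distributions. These figures rest on equal rater marginals and an even spread of the non-zero codes.

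The correction should be made before any reliability figure is reported. It does not affect the trial's hypothesis tests or sample size, and the protocol sets no reliability threshold that a corrected figure could fail.

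**What to change.** Call the printed formula percent agreement, and state what counts as an agreement on the 0–6 scale: the same code, or codes within one point. As the reliability coefficient, report kappa as (Po − Pe)/(1 − Pe) on the item-by-interval codes that both raters produce. Because the codes are ordered, a weighted kappa with its weights stated is preferable. Percent agreement can be reported beside it under its own name.

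The cost is one or two sentences and no new data, since kappa uses the same paired codes. Two consequences should be expected. An unweighted kappa will be lower than the percent agreement unless agreement is perfect, while a weighted kappa may be higher or lower. Codes within one lesson are not independent, so any standard error that treats them as independent would be too small.
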